## Appendix

### CTCA PROTOCOL AND LOCAL CRF AT TIME OF ACQUISITION

#### ➤ Objectives of Cardiac and aortic CT

- To estimate scores of calcification in each main coronary arteries (LM, LAD, Cx, RC), in aortic valve and in each segment of the thoracic aorta (ascending, arch and descending aorta) by using non enhanced CT.
- To estimate plaque and stenosis in all the 16 coronary artery segments by using CT angiography.
- To estimate global score per artery and per patient of calcification and plaque along coronary arteries and thoracic aorta.
- To estimate evolution of such scores between basal CT and CT at 2 years after XRay radiation.

#### ➤ Protocol

##### 1. Non enhanced CT

- **Data acquisition parameters:**
  - Slice collimation 0.5 - 0,6 mm (the smallest one)
  - Tube voltage 120 kV.
  - Tube current dependent on local expertise, typically 50-100 mAs
  - Diastolic imaging
  - Please note heart rate during scan acquisition, or save ECG's during acquisition in the patient folder.
- **Acquisition range:**
  - Include the entire heart and thoracic aorta within the field of view
  - Cranial demarcation: origin of supra aortic branches
  - Caudal demarcation: at least until RV/LV apex, including all pericardial adipose tissue (or more caudal).
- **Reconstruction process**
  - One series with the conventional local calcium score method including 2.4 to 3- mm slice thickness, associated with 1.2-1.5 increment (half the slice thickness) and 220 mm FOV; conventional reconstruction without iterative reconstruction.
  - Second series with 1 mm thick slices with 0.5 mm increment and 220 mm FOV and some iterative reconstruction, leading to close signal to noise ratio regarding the first 2.4-3 mm slice thickness series (the iterative reconstruction will be fixed in each center at the beginning of the study in relation with the corelab).

➤ **Enhanced CT**

- **Data acquisition parameters:**
  - Slice collimation 0.5 - 0,6 mm (the smallest one)
  - Tube voltage 80 - 120 kV
  - Tube current dependent on local expertise and tube modulation
  - Diastolic imaging, including RR interval coverage from to 30 to 80%
  - Please note heart rate during scan acquisition, or save ECG's during acquisition in the patient folder.
  - Injection: quantity, rate depending on patient size and circulation; 100 ml of maximal volume of a solution with  $\geq 350$  ml/l of a iodinated contrast medium.
  - Betablockers if Heart rate  $> 60$  /min
  - Sublingual Nitrate always
  
- **Acquisition range:**
  - Include entire heart with all coronaries within the field of view (the aorta is not required here)
  - Caudal demarcation: at least until RV/LV apex
  
- **Reconstruction process**
  - One series with 0.5 - 0.625 mm and half slice thickness increment with 220 mm FOV and some iterative reconstruction and optimal filter based on the local expertise and CT system. The series will included different ECG timing between 30 to 80% of the RR interval

➤ **Local CRF at time of CT Acquisition**

Inclusion Number: .....

Study Date:.....

Date of Birth: .....

Weight :.....

Height : .....

Name and version of the of the CT system:

- Siemens version: .....
- General Electric Health Care , version:.....
- Toshiba, version:.....
- Philips, version :.....
- Other to precise: .....

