### 7.2. Before start of treatment protocol

About 1 to 2 weeks before the start of radiotherapy, during the visit for the RT planning-CT, women agreeing to participate in the study will give their signed written informed consent form and will then be considered as included. Cardiac MRI will not be mandatory for inclusion in EARLY HEART Study (in contrast with ECHO-ST, CT and BLOOD).

► See *CRF ELIGIBILITY*, *CRF CANCER*, *CRF planned RT* and *CRF CARDIOLOGY*, in appendix for further details

From this inclusion visit on, women's follow-up protocol will be realized. Before start of RT the following interventions will have to be performed:

- Cardiac imaging:
  - An electrocardiogram to detect any arrhythmia followed by an Automated 2D-speckle-tracking echocardiography (ECHO-ST) the most commonly used modality to evaluate myocardial dysfunction and a new technique of assessing myocardial deformation;  
► See *CRF ECHO-ST* in appendix for further details
  - Computed tomography (CT) by using both low dose non enhanced and enhanced CT scans to evaluate coronary artery lesions by assessing morphological information including plaques and stenosis of the arteries, and determination of the CAC score;  
► See *CTCA PROTOCOL* and *CRF* in appendix for further details
  - Cardiac magnetic resonance imaging (MRI) for the measurement of ventricular function, size of the two heart chambers, and wall thickness; tissue characterization by delayed enhancement; and pre-/post-contrast T1 mapping mapping and pre contrast T2 mapping of the left ventricle.  
► See *MRI PROTOCOL* and *CRF* in appendix for further details
- Circulating biomarkers (BLOOD) will be based on a panel of circulating classical and novel blood-based biomarkers (see 7.5 *Blood samples for biomarkers analysis* for further details)

Furthermore, toxicity will be assessed according CTCAE 4.03 and patient rated outcome

measures. ► See *CRF TOXICITY in appendix for further details*

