### **7.4. Subsequent follow-up**

During subsequent follow up imaging and circulating biomarkers will be assessed at specific time points after RT up to 24 months:

- At the end of RT: BLOOD.
- Six months after RT: ECHO-ST, MRI, BLOOD.
- Two years after RT: Electrocardiogram and ECHO-ST, MRI, CT, BLOOD.

Furthermore, in addition to routine follow-up of patients in each center, acute and late toxicity will be assessed according CTCAE 4.03 and patient rated outcome measures at the end of RT, 6 months, and 24 months after RT.

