## 10. REPORTING ADVERSE EVENTS

This is a prospective observational cohort study in which radiotherapy and other oncologic treatments will be performed according to current standard of the participating centres without additional risks.

Serious adverse events related to blood samples or cardiac imaging exams are not expected. The subjects with possible abnormal findings are referred for further examination in accordance with normal procedures in each country.

Minor adverse events are those related to blood samples and cardiac imaging exams.

- Blood collection (pain at veins at the elbow, allergy to products used to clean the skin, hematoma)
- Echocardiography is based on the use of ultrasound. This is a non-invasive method of investigation, non-traumatic and painless. It can be repeated and there are no contraindications. It has not known side effects. It lasts about 15 minutes.
- The CT lasts about 20-30 minutes. The CT requires the injection of iodinated contrast with contraindications (renal failure, allergy). The injection of iodinated contrast material is made in compliance with the contraindications of the latter. The place of injection is done simply at the arm vein. Potential side effects of iodine contrast include flushing, and (mild) skin rash.
- For CT, patient is subject to a scanning X-ray beam. This examination is relatively simple, painless, and safe if one respects the contra-indications. The examination can be done as an outpatient without hospitalization. In terms of radiation dose, the latest techniques in cardiac CT achieve very low levels of radiation, equivalent to one to two years of natural background radiation (average of 2.4 mSv / year), considered acceptable for exam screening for which the radiation-induced risk should be minimal or nil.
- Nitroglycerine may be administered prior to the CT angiography, which is a safe and often used medication for patients with CAD. Side effects include flushing, headache and hypotension, and will not be given to patients with a low blood pressure, left ventricular outflow obstruction or using sildenafil or related medication.
- Betablockers may be used in patients with a fast heart rate before CT. Beta-blockers are used by many patients and regarded as safe. They should not be given to patients with hypotension or conduction disorders as described in the contra-indications to the study.

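### The CT appendix orders nitrate at every enhanced scan, while Section 10 withholds it from three groups of women who remain eligible

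*Combined protocol and SAP*

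**What the plan says.** Two places deal with nitrate before the contrast-enhanced CT.

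- **Appendix, CTCA protocol, Enhanced CT, acquisition parameters:** "Sublingual Nitrate always". Nothing qualifies the line. The line just above it, on beta-blockers, is conditional: it begins "Betablockers if Heart rate" and sets a threshold of more than 60 per minute.
- **Section 10, Reporting adverse events:** "Nitroglycerine may be administered prior to the CT angiography". The same bullet says that the drug "will not be given to patients with a low blood pressure, left ventricular outflow obstruction or using sildenafil or related medication".

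CT is not optional. Section 7.2 makes only MRI voluntary: "Cardiac MRI will not be mandatory for inclusion in EARLY HEART Study (in contrast with ECHO-ST, CT and BLOOD)". Section 7.4 repeats the CT at the last visit: "Two years after RT: Electrocardiogram and ECHO-ST, MRI, CT, BLOOD". Section 8 states that the CT is done for the research study and not as part of standard follow-up.

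**The concern.** The appendix is the technical instruction used when the scan is acquired. Read literally, it tells staff to give nitrate to every woman, including those for whom Section 10 rules it out. The scan is a research procedure, so the drug would be given for the study and not for the woman's own care. What is at stake is patient safety and a consistent instruction across five centres. No consequence for any endpoint, the sample size or the reading of the images is claimed.

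**Working it through.** No formula applies. The check compares the texts and asks whether another part of the plan removes the conflict. It takes the sublingual nitrate of the appendix and the nitroglycerine of Section 10 to be the same premedication.

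**1. The two rules, by type of patient**

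| Patient | CTCA appendix | Section 10 | Compatible? |
|---|---|---|---|
| None of the three conditions | Give | May be given | Yes |
| Low blood pressure | Give | Do not give | No |
| Left ventricular outflow obstruction | Give | Do not give | No |
| On sildenafil or a similar drug | Give | Do not give | No |

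Optional and universal use can coexist in the first row, because giving the drug satisfies both texts. The conflict is confined to the other three rows.

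**2. Does eligibility remove the three groups?**

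- Section 4: 7 inclusion + 7 non-inclusion + 4 exclusion criteria = 18. Naming any of the three conditions: 0.
- CRF ELIGIBILITY: 7 + 7 = 14 lines. Naming any: 0.
- CRF CARDIOLOGY: 3 exclusion prompts (low eGFR, atrial fibrillation, ECG sign of infarction). Naming any: 0.

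The only contraindication to a CT drug among the criteria concerns iodinated contrast. The abnormal-echocardiography exclusion covers ejection fraction, strain, strain rate and wall motion, but not outflow obstruction. Women in the three groups can therefore be enrolled. That is not itself a defect, since Section 10 asks only that the drug be withheld.

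**3. Do the forms catch it?**

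- CRF CARDIOLOGY records blood pressure, ECG and other cardiology treatment at baseline and 2 years. It defines hypertension but has no prompt for low blood pressure, and it does not ask about sildenafil specifically.
- The echo form records outflow tract diameter and velocity time integral, with no flag for obstruction and no action attached.
- The local CT form asks whether nitrate was given, yes or no. It records what was done; it does not say when to withhold.

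None of the forms in the document tells staff to withhold nitrate.

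**4. How often can it arise?** At up to 2 enhanced CTs per affected woman (baseline and 24 months, matching the two additional scans counted in Section 11.4).

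**5. The neighbouring beta-blocker line.** Section 10 says of beta-blockers: "They should not be given to patients with hypotension or conduction disorders as described in the contra-indications to the study". The same lists name neither hypotension nor conduction disorders (0 of 18, 0 of 14, 0 of 3), so the reference leads nowhere. The appendix line depends on heart rate alone. This is a separate, smaller correction, and the nitrate point does not depend on it.

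**The case against.** The best counter-argument is that the two texts can be reconciled. Section 10 is in the body of the protocol and gives a patient-specific prohibition. The appendix line is terse and sits among collimation and tube-voltage settings, so it may mean a default: always, unless prohibited. The yes/no nitrate field supports this, since it would serve no purpose if every scan had to use nitrate. Section 10 also describes the CT examination as "safe if one respects the contra-indications". Harm would require a site to follow the appendix while overlooking Section 10. The participant information and consent pages were not available for this review and may mention the contraindications.

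Much of this stands, and it limits the severity. The Section 10 prohibition remains in force, and nothing here shows that any woman would in fact be given nitrate wrongly. It does not remove the error. The line directly above states a condition for its drug, so a reader has reason to take the unconditional wording of the next line at face value, and nothing in the list points to Section 10. The general remark on contraindications is weak evidence either way: it belongs to the bullet on the X-ray examination, which comes before the nitrate bullet.

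**Conclusion.** The concern holds as a minor internal inconsistency. The appendix instruction is wrong as written for three defined groups and acceptable for all other women. The number of women affected is not given and cannot be derived, and no share is assumed; for each such woman the conflict can arise at up to 2 scans. Confidence is high for the conflict in wording. Any practical consequence depends on a site reading the appendix literally.

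**What to change.** 1. Change the nitrate line in the Enhanced CT list to: *Sublingual nitrate unless contraindicated (low blood pressure, left ventricular outflow obstruction, sildenafil or related medication; see Section 10).* The optional wording in Section 10 can stay as it is.
2. Add to the beta-blocker line: *unless hypotension or conduction disorder; see Section 10.* In Section 10, state those conditions directly and drop the reference to study contraindications that do not include them.
3. Optionally, add a contraindication tick beside the existing nitrate field on the local CT form. The first change resolves the nitrate conflict without it.

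The cost is the wording of two appendix lines and one Section 10 phrase and, if adopted, one tick at each of the 2 CT visits. No additional examination or analysis is required.

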**Non enhanced series:**

Heart rate in bpm:.....

Reconstruction 1 without iteration:

Slice thickness (mm): .....

Reconstruction 2 with 1 mm thick and iteration:  
Iteration mode: expressed as the vendor name with the associated strength:

Enhanced series:

Contrast medium:

Name of the CM:.....

Iodinated Concentration of the CM in g/l : .....

Slice thickness in mm:.....

Heart rate in bpm:.....

Betablockers given at time of CT:      yes      no

Nitrate during CTA:                      yes      no

Reconstruction:

Slice thickness (in mm): .....

Increment (in mm):.....

Iteration mode: expressed as the vendor name with the associated strength: .....

Local Analysis given to the Patients and to the medical staff in charge of the patient:

Is there a  $\geq 50\%$  stenosis of the left main coronary artery: Yes      No

Is there  $\geq 70\%$  stenosis of the proximal Left Anterior Descending artery (LAD1):

Yes      No

If yes : an ischemic test have been done :                      Yes      No

A coronary revascularization has been done:                      Yes      No

**A revascularization means that the patient will be excluded of the study and follow up.**

Other information (calcium score, other CTA results) will be blinded to the clinician team

.....

## Appendix

### CARDIAC MRI PROTOCOL AND LOCAL CRF AT TIME OF ACQUISITION

#### ➤ Objectives of Cardiac Magnetic Resonance

- To estimate systolic and diastolic pressure during acquisition
- To estimate aortic strain at 2 levels (ascending aorta and descending aorta) at the level of pulmonary bifurcation leading to distensibility, local pulse wave velocity estimates.
- To estimate regional pulse wave velocity of the aortic arch (Phase contrast)
- To estimate global function of the left and right ventricle: End diastolic volume, end-systolic volume, and mass and derived estimates with stroke volume, ejection fraction, wall stress and remodeling indices.
- To estimate systolic left and right atrial areas.
- To estimate native myocardial T1 of the left ventricular wall by using 2 small axis levels (base and mid left ventricle).
- To estimate myocardial T2 (oedema) of the left ventricular wall by using the same 2 small axis levels (base and mid left ventricle).
- To detect and quantitate late gadolinium enhancement between 10 and 14 min after Gadolinium injection
- To estimate the myocardial post gadolinium T1 and extra cellular volume at 15 minute at the same 2 small axis levels as native myocardial T1

Most variables will be estimated by the core lab only, by using the same software for included patients.

#### ➤ Protocol

1- Blood sample at the time of CMR to estimate the hematocrit if no other blood sample has been done the same day.

2- Scout

3- Calibration before parallel imaging.

4- Axial SSFP cine series with 8-12 levels to widely cover right and left atrium. 2 to 3 levels per breath hold using 12-16 ; at least 40 cardiac phases / level

5-Small axis SSFP cine series from apex to base with 2 to 3 levels per breath hold.

- i. shim well center on the left ventricle
- ii. FOV < 360 mm,
- iii. At least 50 phases / level
- iv. With high image quality without aliasing or parallel imaging artefact on ventricles

Blood pressure 1 Systolic BP :..... Diastolic BP : .....

6- T1 MAP (MOLLI) before Gadolinium : 2 small axis views (basal/median) 1 level per breath hold : scheme 5(3)3(3)3 with immediate control to obtain high image quality.

7- T2 MAP (3 to 5 echo) before Gadolinium in the same 2 small axis views (basal/median). 1 level per breath hold: with immediate control to obtain high image quality.

8- Aortic SSFP or SPGR 3D series in sagittal and oblique direction to cover the all thoracic aorta (to estimate the length between ascending and descending aorta) in free breathing

9- Contrast enhanced angiography of the thoracic aorta acquired by using sagittal oblique direction during injection of 0.2 mmol/kg gadoterate meglumine (Dotarem, Guerbet, Villepinte, France) and breath hold.

Blood pressure 2 Systolic BP :..... Diastolic BP : .....

10- Aortic SSFP or SPGR 2D I breath hold 1 minute after injection: perpendicular to both the ascending and descending aorta at the level of the pulmonary artery bifurcation, as detected in series 8. Control for the optimal image (shim +++) to obtain high image quality to have an automated detection of aortic borders. Do not hesitate to rescan after gadolinium injection at the end of examination.

Blood pressure 3 Systolic BP :..... Diastolic BP : .....

11- Aortic Phase contrast in free breathing perpendicular to both the ascending and descending aorta at the level of the pulmonary artery bifurcation, as detected in series 7. Only one VPS, VENC = 160 cm/sec, at least 50 cardiac phases, optimal spatial resolution and FOV in less than 2 minutes. Please verify the absence of aliasing (spatial and velocity aliasing). Do not hesitate to rescan at the end of examinationr.

12-Radial SSFP cine series with 2,3- and 4 chamber views of the left ventricle ; at least 40 cardiac phase, optimal FOV.

13- Scout cine IR to detect optimal TI of the inversion recovery sequence

14- Optimal inversion recovery sequence to detect Late Gadolinium enhancement in one or

several breath hold between 10 and 14 minutes post gadolinium injection.

15- T1 MAP post Gado 15-16 minutes : at the two same pre-gadodilium levels.

➤ **Local CRF at time of CMR Acquisition**

Inclusion Number: .....

Study Date:.....

Date of Birth: .....

Weight :..... Height : .....

Name and version of the of the CMR system:

- Siemens version:
- General Electric Health Care , version:
- Philips, version :
- Other to precise:

Intensity of the Magnet

- 3T
- 1.5 T
- other

Hematocrit the day of CMR:..... %

Blood pressures 1 Systolic BP in mmHg :..... Diastolic BP : .....

Blood pressures 2 Systolic BP in mmHg :..... Diastolic BP : .....

Blood pressures 3 Systolic BP in mmHg :..... Diastolic BP : .....

Does the patient present signs of myocardial infarction:

- No
- Yes

If yes, this information should be given to the medical staff in charge of the patient.

Please note that, **when the patient required a vascularization or when a myocardial infarction is detected, the patient should be excluded from the study.**

Open question concerning the transfer of images:.....

**Appendix**  
**BLOOD SAMPLE PROTOCOL**

Blood collection  
≈ 30 ml
